6.2. Key Definitions

Day 1 is the study day on which CoolSculpting procedure is first performed. The study day of an assessment will be calculated as date of assessment - date of study day 1+1. Baseline assessments will be defined as the last assessments before performing CoolSculpting procedure.

6.3. Missing Data

No imputation of missing data will be made for any of the outcome variables.

For the purpose of assigning treatment-emergent AEs (TEAEs), prior and concomitant medications, and concomitant procedures, the followings rules will be applied for partial or missing start dates:

- If the day is missing, the first day of the given month will be used unless the month and year are the same as the month and year of enrollment, in which case the date of enrollment will be used.
- If the day and month are missing, the 1st of January will be used unless the year is the same as the year of enrollment, in which case the date of enrollment will be used.

This document is confidential.

- If the whole date is missing, the date of enrollment will be used.

Imputed dates will not be displayed in data listings.

Other dates will not be imputed.

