9.2. Adverse Events

An AE is any untoward medical occurrence, unintended disease or injury, or untoward clinical signs (including abnormal laboratory findings) in participants, users or other persons, whether or not related to the investigational medical device or the comparator device. This definition includes events related to the procedures involved.

An SAE is defined as an AE that:

- led to death
- led to serious deterioration in the health of the participant, that either resulted in
 - a life-threatening illness or injury; or
 - a permanent impairment of a body structure or a body function, or
 - in-patient or prolonged hospitalization; or
 - medical or surgical intervention to prevent life-threatening illness or injury or permanent impairment to a body structure or a body function; or
 - if a participant becomes pregnant, then spontaneous abortion, fetal distress, fetal death, or a congenital abnormality or birth defect is considered an SAE

AEs will be coded using MedDRA V22.1 or higher.

AEs will be defined as treatment-emergent if they start after the first treatment. AEs with missing or partial dates will be handled according to Section **Error! Reference source not found.** with respect to assigning treatment-emergence. As a conservative approach, AEs are considered treatment-emergent unless there is clear indication that the event occurred before the first treatment in the study. In general, only TEAEs will be included in the summary tables, but all AEs will be included in the listings.

The number of participants and the number of TEAEs will be tabulated by SOC and PT, sorted by the decreasing overall frequency of SOC and then by PT in decreasing frequency within each SOC. For summaries by SOC, PT, and maximum severity, a participant will be counted once at the highest severity level for which the event occurred at the SOC level and the highest severity level for each unique PT within that SOC level. Therefore, participants will only contribute once to each PT and once to each SOC level. Severity will be assessed as mild, moderate, or severe. For summaries by SOC, PT, and maximum

This document is confidential.

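### SAP 6.3 date imputation and the conservative rule in SAP 9.2 give opposite treatment-emergent status to AEs with missing or partial start dates, and the SAP does not say which prevails

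*SAP*

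**What the plan says.** SAP 6.3 (Missing Data) gives its start-date rules a stated purpose: "For the purpose of assigning treatment-emergent AEs (TEAEs), prior and concomitant medications, and concomitant procedures". There are three rules:

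- Day missing: "If the day is missing, the first day of the given month will be used", except that the enrolment date is used when month and year match enrolment.
- Day and month missing: "If the day and month are missing, the 1st of January will be used", except that the enrolment date is used when the year matches enrolment.
- Nothing known: "If the whole date is missing, the date of enrollment will be used".

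SAP 9.2 (Adverse Events) then makes three statements in succession:

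- The definition: "AEs will be defined as treatment-emergent if they start after the first treatment".
- A pointer for incomplete dates: "AEs with missing or partial dates will be handled according to Section", followed by a failed cross-reference in place of a section number.
- A default, described as conservative: "AEs are considered treatment-emergent unless there is clear indication that the event occurred before the first treatment in the study".

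Status matters for reporting: "In general, only TEAEs will be included in the summary tables, but all AEs will be included in the listings". Protocol 8.2.1 collects AEs from consent onward, so pre-treatment AEs can exist and the distinction is needed.

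**The concern.** The imputation anchors on enrolment, but the status it is meant to decide depends on treatment. Where enrolment comes first, an AE with no start date is placed before treatment by construction and fails the 9.2 definition. The 9.2 default points the other way, because a date nobody recorded is hardly a clear sign of earlier onset. Two programmers could each follow the SAP and produce different TEAE tables.

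The error under 6.3 runs in one direction. For events that truly began after treatment, it can only remove them from the TEAE tables, contrary to the SAP's declared conservative intent. Because 6.3 keeps imputed dates out of the listings, a reader could not see why an event was left out.

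The enrolment date is not defined in the visible text. SAP 5.1 ties the Enrolled Population to consent and screening, which suggests a date before treatment. The order in SAP 3.1 (screening, then enrolment, then follow-up) could instead place it at the treatment visit.

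**Working it through.** The plan gives no figure to reproduce, so the check applies the 6.3 rules to possible dates.

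**Inputs.** From the SAP: the three 6.3 rules, the 9.2 definition, and the 8-day screening period (3.1). Assumed: enrolment 1 to 8 days before treatment; treatment dates spread evenly over a 365-day year; true onset uniform over days 0 to 84 (85 days, 12 weeks); dates compared as whole days, with *after* meaning strictly later.

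**Step 1: where the imputed date falls.** There are 365 × 8 = 2,920 combinations of treatment and enrolment date.

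| Recorded start date | Before treatment day | On treatment day | After |
|---|---|---|---|
| None | 2,920 | 0 | 0 |
| Year only, treatment year | 2,912 | 8 | 0 |
| Month and year, treatment month | 2,824 | 96 | 0 |
| Month after the treatment month | 0 | 0 | 2,920 |

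The first three rows are never strictly after treatment, so 6.3 with 9.2's definition makes them non-emergent while the 9.2 default makes them emergent. The last row is emergent under both. A month wholly before the treatment month (432 combinations) is non-emergent under both. The conflict is confined to the first three rows.

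**Step 2: share of true post-treatment AEs classed non-emergent under 6.3.**

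- *Undated:* 100%.
- *Year only:* with k days left in the year, counting the treatment day, the share is min(k, 85)/85. Summing min(k, 85) over k = 1 to 365 gives 85 × 86/2 + 280 × 85 = 27,455, and 27,455/(365 × 85) = 88.5%. By treatment month: January to September 100%, October 89.5%, November 46.5/85 = 54.7%, December 16/85 = 18.8%.
- *Day missing:* for treatment on day d of a month of L days, the share is (L − d + 1)/85. Summing L − d + 1 over the year gives 7 × 496 + 4 × 465 + 406 = 5,738, and 5,738/(365 × 85) = 18.5%. With average L = 30.42, the share is 35.8% for treatment on the 1st, 19.3% on the 15th and 4.0% on the 28th.
- *Day missing, earlier onset:* if onset is confined to days 0–28 the share is 5,713/(365 × 29) = 54.0%; for days 0–14 it is 4,215/(365 × 15) = 77.0%.

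**Step 3: changing only *after* to *on or after*.** This rescues the ties in step 1. Undated stays at 100%. Year-only becomes (27,455 − 85)/(365 × 85) = 88.2%. Day-missing becomes (5,738 − 365)/(365 × 85) = 17.3%.

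**Step 4: enrolment on the treatment day.** All three disputed types are imputed to the treatment day. Strict *after* gives the same 100%, 88.5% and 18.5%; *on or after* gives 0% for all.

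**Examples.** Enrolled 28 January, treated 4 February, AE recorded as February: imputed to 1 February and non-emergent, although 24 of the 28 possible dates (5 to 28 February) fall after treatment. Enrolled 28 December 2021, treated 4 January 2022, AE recorded as 2022: imputed to 1 January 2022 and non-emergent.

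**The case against.** The strongest reply is that the SAP already resolves this. The default sits in the AE section, directly after the sentence on incomplete dates, and matters most when onset is uncertain. An imputed date that is not even shown in listings is a poor candidate for clear evidence of earlier onset. On that reading the specific rule qualifies the general one and nothing is lost. The broken link is editorial, since only 6.3 in the visible text has start-date rules. The enrolment date may be defined in visit schedules that are not shown.

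This reading is plausible, and its target for the broken link is very likely right. But 6.3 claims TEAE assignment as its own purpose, 9.2 defers to that section before stating the default, and no text says whether an imputed date counts as evidence. If the default always wins, the 6.3 rule for undated events does nothing for AEs.

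The reply is also right that the consequence is limited. Protocol 8.2.1 requires the onset date and Protocol 10.3 has missing data queried. Protocol 4.2.1.2 generally keeps mild-to-moderate temporary skin effects, and sensory changes resolving within 12 weeks, out of the AE definition. All AEs are listed, and the ADE and SADE tables in SAP 9.3 are not expressly limited to TEAEs. The analyses are descriptive and the primary endpoint is photographic, so no success criterion depends on TEAE status. This limits the weight of the point but does not remove the contradiction.

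**Conclusion.** The point holds: for three identifiable types of record the SAP gives two opposite classifications and no order of precedence. The loss of true post-treatment AEs from the TEAE tables is 0% if the 9.2 default governs. If 6.3 is followed literally, it is 100% of undated, about 88% of year-only and about 18% of day-missing records. The last figure is higher when onset falls soon after treatment.

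These percentages apply only to AEs with incomplete start dates, whose number the documents do not give, and they rest on the assumed enrolment gap, uniform onset and spread of treatment dates. Fully dated AEs, and partial dates in a later month or year, are unaffected. One participant is 1/42 = 2.4 percentage points of the planned enrolment, and a table row moves by that much only if the participant has no other event in it. The practical effect is probably small, but it should be corrected because it decides which events enter the safety tables and a literal reading defeats the SAP's own intent.

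**What to change.** State in SAP 6.3 and 9.2 that, for AEs, the conservative rule overrides imputation: an AE is treatment-emergent unless the recorded parts of its start date, or a recorded end date, show that it began before first treatment. An equivalent form is to impute Day 1 when the known parts match the treatment month and year, when only the year is known and it is the treatment year, or when nothing is known, provided no end date precedes treatment. Partial dates wholly before the treatment month stay non-emergent; for example, treated 4 February with an AE recorded as January.

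Also define a TEAE as starting on or after the start of first treatment, define the enrolment date, and repair the cross-reference. The *on or after* wording alone is not enough if enrolment precedes treatment (step 3 of the working).

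The cost is a few sentences and a small programming change. The downside is that some incompletely dated pre-treatment AEs will count as TEAEs. For events that truly began in the 8 days before treatment with no earlier end date, these are:

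- day-missing: 2,488/2,920 = 85.2%;
- year-only: 2,884/2,920 = 98.8%;
- undated: 100%.

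The numerators count combinations of treatment date and onset day that share the treatment month or year. AE counts may rise slightly, which is the direction the SAP says it prefers.

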6.4. Visit Windows

Data collected at unscheduled visits that occurred outside the time windows specified in the protocol (e.g., post-dose laboratory tests done on days not specified in the protocol) will be included in the data listings but will not be included in the analyses.

6.5. Pooling of Centres

Data from all investigational centers will be pooled for summaries and analyses.

6.6. Subgroups

Subgroup analyses will be described in section 10.

This document is confidential.

7. Demographic, Other Baseline Characteristics and Medication

7.1. Participant Disposition and Withdrawals

The number of participants who have enrolled into the study, the number and percentage of participants who have had the procedure, the number and percentage of participants who have had all follow-up visits, and the number of participants who discontinued and the reasons for discontinuation will be summarized for Enrolled population.

Reasons for discontinuation from the study may include the following: Physician decision, Protocol deviation, Screen failure, Site terminated by sponsor, Study terminated by sponsor, Technical problems, Withdrawal by participant, Pregnancy, Adverse Event, and Other.

No formal statistical testing will be carried out on these data.

The number and percentage of participants included in each population will be summarized. In addition, the number and percentage of participants excluded from PP population will be summarized descriptively by exclusion reason.

7.2. Demographic and Other Baseline Characteristics

The demographics (age, sex, race [including determination of 1st or 2nd generation Chinese descent]) of participants will be summarized descriptively.

The summary on height, weight, and Body Mass Index (BMI) will be also provided. The number and percentage of participants by BMI category (normal >=18.5 to <25, overweight >=25 to <=30) will also be provided.

Age at Day 1 = (Day 1) visit date - date of birth + 1) / 365.25 and truncated to complete years.

Height (in cm) = height (in inches) * 2.54

Weight (in kg) = weight (in lbs) * 0.4536

BMI (kg/m²) = Weight(kg) / [Height(m)²]

Demographic data will be summarized for the safety and PP populations.

7.3. Medical History

Medical history will initially be coded using Medical Dictionary for Regulatory Activities (MedDRA) V22.1 or higher.

Medical history data will be summarized for the Safety Population. System organ class (SOC) terms are sorted using alphabetical order and preferred terms (PT) are sorted in decreasing frequency within SOC based on the number of participants.

7.4. Prior and Concomitant Medication

Prior medication is defined as any medication that was started and stopped before the date of first CoolSculpting procedure.

This document is confidential.

Concomitant medication is defined as any medication that was taken on or after the date of first CoolSculpting procedure.

Prior and concomitant medications will be coded using World Health Organization Drug Dictionary Global (WHO DD Global) B3 September 2019.

Prior and concomitant medications will be summarized for the Safety Population by presenting the count and percentage of participants treated with each type of medication. Medications will be classified according to ATC categories (ATC Level 2) and the preferred name (generic name) sorted by the decreasing overall frequency of ATC level 2 category and then alphabetically by the preferred name within ATC level 2 category.

Missing/partial dates will not be imputed and listing/table will distinguish concomitant versus prior medications.

7.5. Concomitant Procedures

All concomitant procedures will be listed.

7.6. Protocol Deviations and Violations

Major protocol deviations (PDs) will be determined before database lock.

A deviation is any non-adherence to study procedures that does not result in additional risk to the participant (eg, participant missed a visit). Protocol deviations may or may not be required to be reported to the Institutional Review Board (IRB); however, they must be recorded on the source documentation as well as in the Clinical Trial Management System (CTMS) and may be reported and reviewed in conjunction with the progress report as part of the annual review process.

The process of recording and reporting PDs must be agreed with the sponsor before data collection starts.

PDs will be tracked in CTMS. The following CTMS PD categories will be utilized:

- Inclusion / Exclusion Criteria
- Informed Consent / data privacy: ICF not signed or signed late
- Study procedure: Site staff authorization, delegation, training
- Study procedure: missed procedure or visit

The protocol Deviations Report will be reviewed monthly during internal clinical team meetings as well as monthly during sponsor team meetings to identify any trends and action needed, if applicable.

This document is confidential.

8. Effectiveness Analyses

Photography: A series of baseline and follow-up photographs of the treatment areas will be taken using standardized set up, lighting, and camera settings to ensure consistency. Image files will be stored electronically by Allergan in addition to vendor and indexed by participant identifier. Copies of participant photographic data will be filed at the clinical site. Photos will be reviewed by a blinded independent panel of physician reviewers with expertise in the areas of dermatology and/or plastic surgery. All photographs will be blinded by removing the participant identification and dates of the photographs. The reviewers will be presented with two series of photographs for each treatment area, the pre-treatment and the post-treatment series, and asked to select the series representing the pre-treatment photographs. The order in which the photographs are presented will be randomized by participant. The order in which the pre- and post-treatment series are presented will also be randomized. The reviewers will be asked to select the baseline photograph series for each treatment area and record their data on individual data collection forms provided by the Sponsor.

Participant Satisfaction: Participant satisfaction data will be collected via written questionnaires at the final 12-week follow-up visit. These questionnaires have been developed based on questions used in previous CoolSculpting studies and modified to pertain to specific body areas treated (upper arms and inner thighs). One or two questionnaires will be provided depending on the body areas treated (upper arms and/or inner thighs). For the upper arm participant satisfaction questionnaire, see Appendix 20.1. For the inner thigh participant satisfaction questionnaire, see Appendix 20.2

Caliper Measurements: Caliper measurements of the treatment areas will be taken at baseline and at 12-weeks post treatment. After the treatment area is identified and marked, the thickness of the fat layer will be measured using a caliper at the middle of the fat bulge. For each treatment area, three measurements will be taken and recorded. The average of the three measurements will be calculated.

The primary effectiveness analysis will be based on the PP population.

8.1. Primary Effectiveness Analysis

The number and proportion of arms with correct identification of baseline vs. 12-week images of the upper arms by at least two out of three blinded, independent reviewers. Success will be defined as at least 75% correct identification of the pre-treatment images. The corresponding two-sided exact 95% CI of the proportion of arms with correct identification will be summarized.

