9.3.2.1 Primary Effectiveness Analysis

The number and proportion of participants with correct identification of baseline vs 12-week images of the upper arms by at least two out of three blinded, independent reviewers and the corresponding 95% CI of the proportion of participants with correct identification will be summarized.

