3.3. Determination of Sample Size

In this study, both arms and thighs will be evaluated by independent raters. The independent raters' evaluations will be combined into one clinical judgement on each arm and thigh. The evaluations on arms and thighs will be considered as independent.

A previous study described that the rate of correct identification was 83%. Using 75% as the lower bound of the two-sided exact 95% confidence interval (CI), the $\frac{1}{2}$ -width of the two-sided exact 95% CI will be 8%.

This document is confidential.

Based on these assumptions, we will need 60 evaluable arms or 32 evaluable participants for the arm evaluations with the assumption that less than 10% of participants have only one arm evaluation available. The same number of participants for thigh evaluations will be needed.

With an assumption that only 80% of all participants will have both arms and thighs treated, we will need 38 evaluable participants in total for the study. Adding a 10% attrition rate, we will need to enroll 42 participants in the study.

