3.5. Administration of Study Medication

[figure not shown]
Participants will undergo CoolSculpting treatment(s) in an outpatient clinical setting using CoolAdvantage and/or CoolAdvantage Petite applicators. Each participant will undergo a single treatment session that comprises timed segments of cooling followed by 2 minutes of manual massage. Each treated arm will have up to two timed segments (or cycles) in the treatment session, each treated thigh will have one timed segment (or cycle) in the treatment session. Treatments will be administered according to the Canadian CoolSculpting System User Manual.

[figure not shown]

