1. 'Day 1' is used in this SAP for the study day where 'Day 0' is used in the protocol.
2. As per section 9.2 of the protocol, safety population was defined as 'The safety population will consist of all the treated participants with at least one safety evaluation after the treatment'; AT was defined as 'The AT population will consist of all treated participants regardless of weight change, etc.'. These two populations will consist same participants . Therefore, in the SAP, only one of them is defined as 'The safety population will consist of all the treated participants'.
3. Sample size is calculated based on number of arms. 'participants' is a typo in the protocol. So, the term 'participants' is replaced by 'arms' appropriately. Similarly, 'participants' is a typo in the protocol for primary and secondary effectiveness analyses. The term 'participants' is replaced by 'arms' or 'thighs', respectively. These are administrative changes.

This document is confidential.

[figure not shown]
13. Reference List

To be updated.

[figure not shown]
This document is confidential.

[figure not shown]
This document is confidential.

This document is confidential.

[figure not shown]
This document is confidential.

17. Index of Figures

No Figures

This document is confidential.

[figure not shown]

This document is confidential.

[figure not shown]
19. Table, Listing, and Figure Shells

This table, figure and listing shells will be provided as a separate document.

[figure not shown]
This document is confidential.

[figure not shown]
This document is confidential.

[figure not shown]
This document is confidential.

This document is confidential.

This document is confidential.

This document is confidential.

This document is confidential.

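### The primary exact 95% CI counts a participant's two arms as independent, so it is too narrow once left-right correlation exceeds roughly 0.15 to 0.2

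*SAP*

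**What the plan says.** Protocol 9.3.2.1 counts participants: "the corresponding 95% CI of the proportion of participants with correct identification will be summarized". SAP 8.1 counts arms and names the method: "The corresponding two-sided exact 95% CI of the proportion of arms with correct identification will be summarized". SAP 12 treats the Protocol wording as a typographical error: "The term 'participants' is replaced by 'arms' or 'thighs', respectively. These are administrative changes".

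SAP 3.3 sizes the study on arms, starting from a rate of 83% and "Using 75% as the lower bound of the two-sided exact 95% confidence interval (CI"). It asks for 60 evaluable arms or 32 evaluable participants, "with the assumption that less than 10% of participants have only one arm evaluation available". On independence it has one sentence: "The evaluations on arms and thighs will be considered as independent".

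On treatment and image review, SAP 3.5 says "Each participant will undergo a single treatment session", and the photography paragraph at the start of SAP 8 says "The order in which the photographs are presented will be randomized by participant".

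SAP 8.2 (thighs) and SAP 10 (generation subgroups) use the same exact interval on limbs. Neither document gives a left-right correlation, a design effect, a clustered interval or a participant-level sensitivity analysis.

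**The concern.** The exact binomial interval is valid for independent units. Here about 60 arms come from about 32 people, and the two arms of one person share the person, the treatment session and any weight change within the 5% per-protocol limit. Photograph order is randomized by participant, and the text does not say whether left and right are shown to the reviewers separately.

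The independence sentence does not settle this. If it means arms versus thighs, left versus right is not covered. If it means every limb, it is an assumption without justification.

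The Protocol's participant-level interval had no such problem. Moving the unit to arms changes what the interval assumes, so it is more than an administrative correction.

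This interval is the only measure of uncertainty on the primary endpoint, and SAP 3.3 ties its lower limit to 75%, so readers can be expected to compare the two.

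**Working it through.** **The plan's own figure.** With p = 0.83 and half-width h = 0.08, n = z²p(1−p)/h². For z = 1.96, n = 3.8416 × 0.1411 / 0.0064 = 84.7, so 85 arms, not 60. Only z = 1.645 gives 60 (2.706 × 0.1411 / 0.0064 = 59.7). That is a separate matter. The plan's 60 arms are used below because they are what it expects to analyse.

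**Inputs.**
- SAP 3.3: 60 arms, 32 participants, rate 83%, reference value 75%.
- SAP 8.1: two-sided exact 95% interval, taken as Clopper-Pearson.
- 60 arms in 32 people means 28 pairs and 4 singles (2 × 28 + 4 = 60). That is 12.5% single-arm, slightly above the plan's limit of under 10%, so 29 pairs and 3 singles (9.4%) was also run.
- The left-right correlation ρ is not in the documents, so it is an assumption shown from 0 to 1.

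**Model.** P(both arms correct) = p² + ρp(1−p); single arms are independent. The exact distribution of the number of correct arms follows by enumeration. The design effect is (60 + 56ρ)/60.

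**Coverage and exceedance of the planned interval (28 + 4).** The last column is the chance that the lower limit lies above 75% when the true rate is 75%; its nominal maximum is 2.5%.

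| ρ | Coverage at 83% | Average coverage, rates 75–90% | Lower limit above 75% at a true rate of 75% |
|---|---|---|---|
| 0 | 96.3% | 96.7% | 2.1% |
| 0.15 | 94.9% | 95.5% | 2.9% |
| 0.3 | 93.4% | 94.1% | 3.7% |
| 0.5 | 91.4% | 92.2% | 4.8% |
| 1 | 85.7% | 87.4% | 7.9% |

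With 29 + 3, coverage at 83% differs by at most 0.4 points, and the last column becomes 1.8, 2.5, 3.2, 4.3 and 7.4%.

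**Break-even.** The exact interval is conservative under independence, and that margin absorbs some correlation. Coverage reaches 95% at ρ = 0.14 for a true rate of 83%, 0.18 for 80%, 0.26 for 85%, 0.27 for 90%, and about 0.2 averaged over 75–90%. Because counts are discrete, single rates give values from 0.05 to 0.43. Below break-even the interval is not too narrow.

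**Effect on reported limits.** Clopper-Pearson on effective n = 60 / design effect. At ρ = 0.3 the design effect is 76.8/60 = 1.28 and effective n is 46.9; at ρ = 0.5 they are 88/60 = 1.467 and 40.9.
- 50/60 correct: 71.5–91.7% as planned, 69.6–92.6% at ρ = 0.3, 68.4–93.1% at ρ = 0.5.
- 52/60 is the lowest count whose planned lower limit clears 75% (75.4%). On effective n that limit is 73.5% at ρ = 0.3 and 72.4% at ρ = 0.5, and 53/60 and 54/60 respectively are then needed.

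**The case against.** The strongest reply is that no decision depends on this interval. SAP 2 makes all analyses descriptive, and success in SAP 8.1 is a rule on the point estimate. The exceedance probabilities therefore describe a test that the plan does not run. Near the planned rate, the comparison with 75% does not change either: 50/60 gives a lower limit of 71.5% even under independence. Only a narrow band flips: 52/60 at ρ = 0.3, and 52 or 53 of 60 at ρ = 0.5. This stands, and it limits the consequence to overstated precision.

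Second, ρ is unknown. At 0.15 the loss is trivial, and a fall to 91–92% needs ρ near 0.5. That also stands, as does the point that break-even varies widely by true rate. The threshold of 0.15 to 0.2 is a summary, not a sharp cut-off.

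Third, SAP 3.3 provides one combined judgement for each limb. That fixes the unit of rating but does not remove correlation between two limbs of one person.

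Fourth, the threshold does not carry over to small subgroups. With 8 pairs and 1 single, the plain interval still covers 96.0% at a rate of 83% and ρ = 0.5, and a clustered one covers about 99%. In a half-size subgroup (14 pairs, 2 singles), however, the plain interval falls to 93.6% at ρ = 0.5 and 87.1% at ρ = 1. Clustering there is conservative, sometimes heavily, but not unsound.

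**Conclusion.** The concern holds and should be fixed. The planned primary interval assumes independent arms, the documents do not justify that for left versus right, and the change of unit that created the problem is recorded as administrative. If ρ exceeds about 0.2 on average over plausible rates (0.14 at 83%), coverage is below 95%: about 91–92% at ρ = 0.5 and 86–87% at ρ = 1. The arm-level proportion and the 75% verdict do not change.

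The size rests on three assumptions: a common ρ, which the documents do not give; 60 arms from 32 participants; and the Clopper-Pearson form of the exact interval.

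**What to change.** Keep the arm-level estimate and the 75% rule. Replace the plain interval in SAP 8.1 with a pre-specified participant-clustered one, for example:

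- Clustered variance = k/(k−1) × Σ(correct arms − own arms × p)² / arms², summed over the k participants, with p the observed proportion.
- Design effect = clustered variance / [p(1−p)/arms].
- Clopper-Pearson on effective n = arms / design effect, capped at the number of arms.
- If all arms are correct, report the lower limit that one miss in a two-arm participant would give; mirror this if none are correct. Then 60/60 gets 91.0%, never worse than 59/60 (91.0% or 90.8%).

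The data set the width, so no ρ has to be assumed. For 50/60 with 28 pairs and 4 singles:
- 9 split pairs and 1 single miss: 71.5–91.7%, unchanged.
- 2 both-wrong pairs, 5 split pairs and 1 single miss: 69.1–92.8%.
- 4 both-wrong pairs, 1 split pair and 1 single miss: 66.2–94.0%.

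At a true rate of 83%, coverage of this interval is 96.8, 96.4, 96.2, 96.3 and 97.8% at ρ = 0, 0.15, 0.3, 0.5 and 1. Its lowest value over the settings run is 93.6% (rate 90%, ρ = 0.8), where the plain interval has 90.1%. It is narrower than the plain interval in none of the 2,175 possible outcomes. Another standard clustered interval would also serve, if it is named in advance.

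Use the same method for the thigh interval (SAP 8.2) and the generation-subgroup intervals (SAP 10). Where a subgroup has one participant, k/(k−1) is undefined, so give the count only. State in SAP 3.3 whether independence is meant to cover left versus right. In SAP 12, list the move from participants to limbs as a change to the analysis.

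The cost is SAP wording and a few lines of code, with no new data. If ρ is truly 0 at a rate of 83%, the average half-width rises from 10.05 to 10.45 points.
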